The principal investigator ([name]) is a primary care pediatrician who has conducted innovative, reading-related research involving young children with a high degree of success, including randomized trials of home reading environment⁴⁵, development of clinic-based screening tools,⁴⁶ video observations of parent-child reading quality,^{19, 20} and the application of functional MRI to explore the effects of home reading environment,

including shared reading quality, on the developing brain.^{19, 20, 37} Addressing younger infants and toddlers in this study during critical stages of early brain development is a natural extension of this work, and would build on a cohesive eco-bio-developmental model⁴⁷ of the influence of home reading environment on emergent literacy. Prior to the launch of this study, the principal investigator will travel to the CHC@CCMC host site to discuss and train the study team in this protocol, specifically the research coordinator, including practice “role play” sessions.

A full-time clinical research coordinator (CRC) will be recruited for this study in cooperation with the Weitzman Institute, a community-based research center affiliated with CHC@CCMC dedicated to quality improvement and research in primary care for the underserved. The CRC will be trained in this study protocol via the principal investigator ([name]), the on-site medical director and co-principal investigator ([name]), and a co-investigator from the national ROR program ([name]). The CRC will then recruit the 248 children in our desired age ranges (124/category) via convenience sampling during regularly scheduled well-child visits. Full enrollment within 6 months is feasible given historical well-visit volumes for these ages (40/month meeting enrollment criteria) at the participating clinic at CHC@CCMC. The CRC will optimize enrollment efficiency factoring scheduled well-visit volumes and demographic needs (age), via advance communication with clinic managers. Biostatisticians affiliated with Children, Inc., will perform all required statistical analyses, accessing data via a secure REDCap database housed at CCHMC Division of Biomedical Informatics. Application developers aligned with Children, Inc., will be available to perform any required technical modification or “troubleshooting” of the RS application.

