Rx for Success Application (RS): The RS mobile application (app) was developed by Children, Inc. The app is designed to be informational and motivational with both video and cueing content. The app uses a, “View It, Cue It, Do It” model that allows parents to quickly download the free smartphone app, view brief videos of the age-indexed, research-based language enrichment practices; and regulate a text message cueing program. The app uses three motivational strategies in the cueing program: 1) Personalization; 2) Gamefication; and 3) Social media. Videos embedded in the RS app provide a summary of DR tailored for the child’s age, and suggestions for encouraging verbal interactivity and social-emotional engagement through dialogic reading. Key behaviors reinforced by the app include discussing the story before reading to build interest and enthusiasm, followed by interactive reading modeled by the acronym PEER:⁹ 1) **P**rompt the child to say something about the story, 2) **E**valuate what the child says or does, 3) **E**xpand on what the child says or does, and 4) **R**epeat and reinforce associations or responses. The acronym CROWD reflects simple types of prompts that can encourage the child’s involvement in the story, which gradually apply with age and development: 1) **C**ompletion (of a sentence), 2) **R**ecall earlier aspects of the story, 3) **O**pen-ended questions, 4) **W**h- questions, and 5) **D**istancing (relate the story to the child’s life). Finally, the RS app encourages the caregiver to review the story with the child after it is finished to reinforce the book sharing experience.

[figure not shown]
While highly impactful independently, this research will also provide valuable pilot data for a larger, longitudinal study exploring means to improve home

reading environment during early childhood via the ROR model incorporating traditional and novel technologies, especially in underserved populations.

8) Study Design

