- Comfortable speaking English during their WCC and reviewing/comprehending study materials without a translator, including informed consent.
- Functional literacy in at least one primary caregiver, defined as the ability to navigate the RS application, read prompts provided by the RS application (targeted 6th grade reading level as estimated via the Readable.io website), and understand/provide informed consent, administered in English.
- Possession of a smartphone or tablet device capable of downloading, installing and utilizing the RS application.

Twins will be excluded from the study, to minimize confounding.

In the case of 2 eligible siblings presenting at the same visit (i.e. 6 month old and 18 month old), both may be enrolled, though will be randomized to the same group to minimize confusion and confounding.

In the case of an eligible sibling presenting after another sibling has been enrolled, this second child (and any other siblings) will be ineligible, to minimize confounding via a training effect.

b) Study Endpoints*

Outcomes of interest for this study (6 months post-intervention) are as follows:

a) **Descriptive Statistics:** Descriptive statistics will be used to summarize parent-child demographics, language and social-emotional testing scores (LENA Snapshot, DECA-I/T excerpted items), home reading environment/dialogic reading/cognitive-language attitudes (StimQ-P READ and PVR excerpted items, DialogPR-I/T), and screen time (ScreenQ). Group-wise comparisons will be performed to determine any differences

between randomization groups. Spearman's rank correlation will then be used to assess correlation between variables of interest at baseline and 6-month follow-up visits, applying age and gender as covariates.

b) **Pre-post intervention cognitive-behavioral outcomes:** Outcomes of interest will involve group-wise statistical comparisons pre-post intervention of language, social-emotional development, and home reading practices/attitudes measures. All repeated measures (LENA, DECA-I/T excerpted items, StimQ READ and PVR excerpted items, DialogPR, ScreenQ, reading attitudes) will be examined via paired t-test, Wilcoxon signed-rank test, and McNemar's tests. Association between home reading environment and screen time and language and social-emotional testing scores will be assessed by correlation coefficient and applied in general linear regression models, applying age and gender as covariates.

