c) **Satisfaction with RS and frequency of use:** responses on surveys administered to caregivers at the 6-month follow up visit (12 or 24 months old) will be analyzed, including frequency and ease of use (e.g number of "push" notifications).

d) **Feasibility:** Caregiver satisfaction with RS will be conducted via closed and open-ended survey items administered via the CRC, including barriers to use (e.g. cell phone minutes, clinical flow, data plan), time of administration, and suggested means of improvement.

There are no safety endpoints involved with this study.

c) Procedures involved in the Human Research*

Randomization: Following agreeing to participate and providing informed consent, families in both age groups (infant and toddler) will be assigned to either the intervention or control cohort (62 in each cohort for each group) by research coordinators using a spreadsheet with assignment codes determined by computer-generated random numbers provided by a biostatistician (Group A and Group B). Participants will be blinded as to group assignment and not advised as to differences in intervention between groups, for the purposes of the research. The CRC will not be blinded, as this is infeasible. Statisticians will be blinded as to the definition of Group A or B (i.e. which is the intervention), to ensure objectivity in analyses.

Testing and Surveys: Testing and survey administration will be performed in a private part of the waiting area or clinic exam room, *in the following order of preference*, mindful of patient/clinic flow:

- 1) Before seeing the provider for the scheduled WCC.
- 2) After the provider has completed their exam, but before lab tests or shots.
- 3) After lab tests and shots, if needed.

Of note, all surveys and measures are administered to the parent (i.e. parent report), none directly administered to or involving the child.

At all times, deference will be given to clinic staff and the family to maintain the flow of the visit. The CRC will approach the clinic manager, supervising nurse, or clinical provider in charge of clinic flow on the morning of each clinic session, to discuss preferred strategies, including designated exam room for consent and survey administration. If unable to complete all data collection, the family will be free to go at their discretion and data collected will be utilized to the extent possible. The order of administration will prioritize items that are most important to achieve our study aims,

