4) **StimQ-Infant/Toddler (excerpts, 2 minutes)** is a validated assessment of cognitive stimulation in the home. *For this study, to keep administration time brief, 5 items excerpted from the READ and Parental Verbal Responsivity subscales will be administered*, assessing access to books, frequency of shared reading, and verbal interactivity in the home. In addition, caregivers will be asked to list their 3 favorite activities to do with their child at home (open ended, coordinators noting whether reading is included), as in Needlman, et al (2005). Estimated administration time is 2 minutes.

5) **DialogPR-I/T (2 minutes)** is an 8-item parental report assessment of shared reading quality created by the principal investigator for caregivers of children age 18 months and up, and a related version for younger infants (DialogPR-I/T) based on a dialogic reading conceptual model. Initial validation involving a low-SES population⁴⁶ showed strong psychometric properties. Estimated administration time is less than 2 minutes.

6) **ScreenQ (2 minutes)** is a novel assessment of screen-based media use in the home developed by the principal investigator, consisting of 10 evidence-based⁵⁰⁻⁵² items reflecting access to screens, frequency of use, content, and interactivity. This measure was recently pilot tested and psychometrically refined in a diverse sample of preschool-age children, and is applicable for ages 0-9 years. Estimated administration time is 2 minutes.

[figure not shown]
A flow diagram summary of enrollment, consent, and baseline testing is provided below:

Administered at the follow-up visit (post-intervention; approximately 12 and 24 months):

At the 12-month (11 to 15 month) or 24-month (23-27 month) well-child visit, the LENA, DECA-I/T items, StimQ-I/T items, DialogPR, and ScreenQ will be repeated. Caregiver surveys of frequency and ease of use of the RS app will also be administered. The CRC will contact families by phone and text message approximately 1 month in advance of the follow-up visit to remind them of the date and time, and importance to attend this visit. Estimated administration time is ~16 minutes.

A flow diagram summary of follow-up testing is provided below:

Dialogic Reading Intervention (DRI): For families assigned to the DRI group, in addition to customary ROR procedure in the clinic, the DRI will involve:

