(not via cellular text message so will not count against participant's data plan). Key behaviors reinforced by the app include discussing the story before reading to build interest and enthusiasm, followed by interactive reading modeled by the acronym PEER:⁹ 1) **P**rompt the child to say something about the story, 2) **E**valuate what the child says or does, 3) **E**xpand on what the child says or does, and 4) **R**epeat and reinforce associations or responses. The acronym CROWD reflects simple types of prompts that can encourage the child's involvement in the story, which gradually apply with age and development: 1) **C**ompletion (of a sentence), 2) **R**ecall earlier aspects of the story, 3) **O**pen-ended questions, 4) **W**h- questions, and 5) **D**istancing (relate the story to the child's life). Finally, the RS app encourages the caregiver to review the story with the child after it is finished to reinforce the book sharing experience.

c) Monitoring adherence and "dose" of DRI: At the 12 or 24-month follow-up visit, a survey of frequency and ease of use of the RS app, developed by the principal investigator, will be administered to the child's primary caregiver.

Families assigned to the Control group will receive a new children's book regarding limiting screen-based media use (*Baby Unplugged: Play*, [name]/Jones, blue manatee press), which lists AAP screen time recommendations on the back cover.⁴⁸ This will be briefly reviewed by the CRC, in addition to customary ROR procedure in the clinic. A postcard will be provided conveying contact information for the CRC in the event of a change in participant phone number or other contact information. Care will be taken to make the instruction process as brief as possible, to simulate how a pediatric provider or support staff would function in a busy, real-world clinical setting.

d) Data management*

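### The A/B blinding of the statisticians is not assured, because the same analysts also handle app-use data that reveal the intervention code, and nothing keeps those data back until the outcome comparisons are done

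*Protocol*

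**What the plan says.** **The blinding claim.** Section 8(c), Randomization, has families assigned to Group A or Group B from a computer-generated list. It then states: "Statisticians will be blinded as to the definition of Group A or B". The stated purpose is objective analysis. The research coordinator is openly not blinded.

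**Who analyses.** Section 7 states: "Biostatisticians affiliated with Children, Inc., will perform all required statistical analyses". They work from the REDCap database held in Cincinnati. Sections 6, 12 and 19 also place the analysis at or through Children, Inc.

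**Who made the app.** Section 7 states: "The RS mobile application (app) was developed by Children, Inc". Section 8(c), item b) of the intervention list, repeats this.

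**What is analysed about the app.** Section 8(b), item c), makes caregivers' use and opinion of the app an outcome of the trial: "responses on surveys administered to caregivers at the 6-month follow up visit (12 or 24 months old) will be analyzed". Item d) covers feasibility: "Caregiver satisfaction with RS will be conducted via closed and open-ended survey items administered via the CRC". It includes barriers to use and time of administration.

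**Where those data come from.** In section 8(c) the intervention list opens with "For families assigned to the DRI group, in addition to customary ROR procedure in the clinic, the DRI will involve". Under item a) the coordinator records the time and feedback from the app-training step. Under item c) comes "a survey of frequency and ease of use of the RS app", given at the follow-up visit.

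**What limits the analysts' data.** Sections 12 and 19 say that downloads are deidentified. No other limit is stated.

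**The concern.** A/B coding hides the arms only while nothing else in the analysts' data tells the two codes apart. Here the people said to be blinded must also summarise data that exist, or make sense, only for families given the app. When those data carry the group code, the code is broken. The protocol does not say whether this happens before or after the language, social-emotional and reading outcomes are compared.

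The analysts' affiliation does not cause the unblinding, but it raises the value of the masking, because analysts linked to the developer would know which arm received the developer's product. They would also have choices to make. The power sections name an ANCOVA with age category and its interaction, while section 8(b) says: "All repeated measures (LENA, DECA-I/T excerpted items, StimQ READ and PVR excerpted items, DialogPR, ScreenQ, reading attitudes) will be examined via paired t-test", followed by Wilcoxon signed-rank and McNemar tests. Choices about emphasis, subsets and incomplete data are what analyst blinding is meant to protect. A reader of the final report would credit the trial with that protection.

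**Working it through.** The protocol gives no figure on this point, so the check traces which fields exist in which arm, who sees them, and when.

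**1. Is any analysed field specific to one arm?** Yes.
- The training time and feedback are items of the intervention list. Control families receive a book and no app (section 8, Study Design; section 8(c)).
- The app-use survey is item c) of the same list. One general sentence in section 8(c), on the follow-up visit, mentions the survey without naming an arm.

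**2. Does that general sentence rescue the masking?** There are two readings.
- *Survey given to intervention families only.* Section 8(c) allocates 62 per arm in each of two age groups, so 62 × 2 = 124 per arm. App records exist for up to 124 participants under one code and 0 of 124 under the other. With the protocol's 10% attrition figure, 124 × 0.90 = 111.6, or about 112 against 0.
- *Survey given to both arms.* Controls were not given the app, so their answers would show near-universal non-use, and the contrast in responses identifies the code.

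On both readings the fields reveal the arm. On the first, a single completed record linked to a code is enough.

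**3. Are the analysts of these fields the blinded statisticians?** Yes. Section 7 gives all analyses to the same group, and no separate analyst is named for the use and feasibility endpoints.

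**4. Does anything stop the fields reaching them with the code, before the outcome comparisons?**

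| Possible barrier | Stated in the protocol? |
|---|---|
| Names and contact details removed | Yes (sections 12 and 19), but this protects identity and does not mask the arm |
| App fields held back or exported separately | No |
| Outcome analyses locked before app analyses | No |
| Different analyst for app data | No |

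**5. Conclusion of the trace.** The masking must end at some point, because the app endpoints cannot be reported without knowing which group had the app. Whether it ends before or after the outcome comparisons is left open, so the protocol asserts a property that it does nothing to secure.

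**The case against.** **The protocol does not describe the export.** A reader might infer that the blinding fails on first sight of the data. That would require the app fields and the group code to arrive together, before the comparisons are run. The text does not say so, and a staged export would be compatible with it. This stands, so failure at first sight is not shown. The protocol nevertheless makes a positive claim of blinding and gives the same people the data that defeat it, so this is more than an operational detail left for later.

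**A/B coding is not the only safeguard.** A reader might infer that it is. Section 6 puts the analysis under the supervision of the principal investigator, who is not at Children, Inc. The power sections name LENA Snapshot as the primary measure, with a baseline-adjusted ANCOVA at two-sided 0.05. This also stands. These measures narrow the room for choice, but they do not mask the arms, and the supervising investigator is not described as blinded.

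**No error rate can be attached.** It is tempting to say that taking the better of two independent analyses raises 5% to 1 − 0.95² = 9.75%. That figure measures multiplicity, which is equally open to a perfectly blinded analyst, so it does not measure harm from unblinding. Moreover, paired tests address change within subjects, while the ANCOVA addresses the difference between arms. They are not two tests of one hypothesis. The objection stands in full, and the figure forms no part of this point.

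**Analyst masking is secondary here.** The unblinded coordinator administers every parent-report outcome, so a larger exposure lies elsewhere. That is fair, and it limits the weight of this point. It is no reason to leave an inaccurate claim in place when the repair is nearly free.

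**Conclusion.** The concern holds in a limited form. The protocol says that the statisticians do not know which code is the intervention, yet it gives those same statisticians app-use, satisfaction, barrier and administration-time data that reveal it once linked to the code. It sets no sequence or separation to prevent this before the outcome comparisons are complete. The blinding is therefore not assured.

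The effect on the trial's results is a risk. No bias is shown, and its size cannot be derived from the protocol. What is clear is the data pattern: up to 124 app records under one code against none, or against near-universal non-use, under the other.

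The conclusion assumes that the app endpoints are analysed by the biostatisticians named in section 7, as the text says, and that few control families use the app. A statistical analysis plan or data-management plan, not available here, might already stage the release. If so, the protocol need only say so.

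**What to change.** Amend section 8(c), Randomization, and section 12 to describe two releases of data to the analysts:

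1. **First release:** study ID, A/B code, age category, gender, baseline demographics, and the baseline and follow-up outcome measures. Gender is needed because section 8(b) uses it as a covariate.
2. **Second release,** only after the between-group outcome analyses are locked and dated: RS-use, satisfaction, barrier, training-time and feedback fields, and the A/B key. The use and feasibility analyses are then run.

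Until the second release, the later fields and the key are withheld from the analysts. Since section 7 describes access through REDCap, the analysts' user rights should match the first release. The coordinator necessarily knows the allocation, and that does not change.

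If the staging is not adopted, the statement that the statisticians are blinded should be withdrawn, so that readers do not rely on it.

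The cost is one extra export, a few sentences of text, and an app-use analysis that comes slightly later. The sample size, visits and measures do not change. The step must be in place before the analysts receive any app-related field, because blinding cannot be restored once the code is known.

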during regularly scheduled well-child visits. This study will be powered based on the primary language outcome measure (LENA Snapshot). For a two-group (intervention/control), pre-post repeated-measure analysis with two age categories (6-12 months, 18-24 months), an ANCOVA model will be applied for both age categories and their interaction, to assess the difference in language scores between intervention and control groups. For this study, at least 180 subjects will be needed to have 80% statistical power to detect slightly greater than medium effect size (Cohen $f=0.30$), controlling for the baseline pre-measurement with a two-sided significance level of 0.05. This effect size was determined considering the 2008 National Early Literacy Panel Report, which examined 16 studies and reported an effect size of 0.6 for dialogic reading on language outcomes ($d=0.6$; Shanahan, et al).⁴⁹ A separate meta-analysis of 18 studies that tested dialogic reading intervention found average effect size for language outcomes and vocabulary of 0.29 and 1.02, respectively.⁸ However, these reports largely involved preschool- and school-age children, and no studies to our knowledge have reported effect sizes of dialogic reading for language in infants and toddlers.

We anticipate that full enrollment for this study within 6 months is feasible given historical well-visit volumes for these ages (40/month meeting enrollment criteria) at the participating clinic at CHC@CCMC. The CRC will optimize enrollment efficiency factoring scheduled well-visit volumes and demographic needs (age), via weekly communication regarding clinic schedules with clinic managers. The CRC will identify the arrival and registration of potential participants by monitoring the daily schedule (in Centricity) to identify well child visits for children of the appropriate age groups, and will greet them in the waiting room. For enrolled patients only, the CRC will also monitor scheduled encounters (in e-Clinical Works) to identify upcoming appointments for the follow-up (post-intervention) visit, and will monitor arrival in Centricity. The CRC will approach families in the waiting area, confirm that the child meets inclusion criteria by age, and present the major aims of the study in plain language:

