particularly demographics, home reading/language environment (StimQ READ/PVR items), language (LENA), and social-emotional development (DECA excerpted items).

Estimated testing/survey administration time is approximately 17 minutes.

Administered at baseline (pre-intervention; approximately 6 and 18 months old):

1) **Demographic Surveys (3 minutes):** During the first visit only, demographic information will be obtained from custodial parents including contact information, type of smartphone or tablet to be utilized including data plan (e.g. unlimited vs limited data), household income, parental education, history of reading difficulty including dyslexia or functional illiteracy, who usually reads to the child at home, primary language spoken at home, daycare attendance, and number of occupants in the home. Estimated administration time for this survey is 3 minutes.

2) **LENA Snapshot (6 minutes)** is a validated, 52-item, evaluation of language skills for infants and toddlers by parental report focusing on well-established milestones associated with expressive and receptive language skills, with a standardized score under 77 suggesting risk for delay. It provides developmental age and percentile ranking information compared to age-matched peers. Correlations with standard measures such as PLS-4 and test-retest correlations average 0.93. Estimated administration time is 3 minutes. Of note, this measure is not directly administered to the child.

[figure not shown]
3) **Devereux Infant/Toddler Early Childhood Assessment (DECA-I/T items; 2 minutes)** is a measure of social and emotional health validated for use in children between 1 month through 36 months, which are strength-based, nationally standardized, and easy to use. The DECA has 4 scales: Attachment/Relationships (18 items), Initiative (11 items), Self-Regulation (7 items), and Total Protective Factors composite. The infant form (1-18 months old) has 33 items, and the toddler form (18-36 months old) has 36 items. *To keep our administration time as brief as possible, we will excerpt 5 items from the attachment subscale* (those most likely to be influenced by shared reading) for this study, and add these item scores to determine a total score. Estimated administration time for these items is 2 minutes.

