- A single CRC to be hired via the Weitzman Institute will be solely responsible for informed consent.
- Informed consent will cover all aspects of the study included on the consent form, in plain English, anticipated to take less than 5 minutes. The ability to comprehend the informed consent documents in plain English without a translator is a requirement for inclusion in this study.

- Non-English speaking families are excluded from this pilot study due to restrictions on time, budget, and the need to minimize covariates such as language spoken at home in our analyses, especially as bilingual children are known to have short-term language delays likely to influence our findings. The RS app is also not currently available in Spanish. In the future, we plan to expand our research to non-English speaking households.
- As this study involves convenience sampling in the waiting area, there is no lag expected between approach for consent, administration of consent, and enrollment in the study for those interested.
- The CRC administering informed consent will emphasize that participation in this study is optional and voluntary, and that their child will receive the same well-child care regardless of participation, including via the Reach Out and Read program.
- Consent from one custodial parent is all that will be required for this research. “Custodial” parent will be defined as with necessary permission to accompany the child to the doctor at the current visit, and who lives with the child at home and would have the opportunity to consistently read to them. As reading with children is generally considered to be beneficial, we feel that permission from one parent is adequate for our study design. If, by small chance, the second parent or custodial caregiver protests this enrollment and requests removal, the child will be removed from the study.
- If the child is accompanied by another family member such as an aunt or grandparent, they will not be enrolled in this study, unless this family member has full-time legal custody of the child, authorized by a court order.
- This study clearly involves children (age 6-12 months and 18-24 months old), by any definition. Children of this age can not reasonably be expected to provide consent or assent, and will not be asked to do so.

16) Process to document consent in writing

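### The English criterion reduces home-language variation but does not remove it, and primary home language is collected without being named in the LENA ANCOVA or the Hypothesis 2b model

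*Protocol*

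**What the plan says.** **Rationale (section 15, Consent process).** The exclusion is explained as follows: "Non-English speaking families are excluded from this pilot study due to restrictions on time, budget, and the need to minimize covariates". Language spoken at home is the example given, with the added reason that "bilingual children are known to have short-term language delays likely to influence our findings". The section also notes that the app is not yet available in Spanish.

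**Operative criteria (section 8a, Inclusion and Exclusion Criteria).** The language criterion is "Comfortable speaking English during their WCC and reviewing/comprehending study materials without a translator, including informed consent". The literacy criterion is "Functional literacy in at least one primary caregiver", defined by use of the app and by consent in English. Neither mentions the language of the home or the child's exposure to a second language.

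**Data collected (section 8c, Demographic Surveys).** The baseline survey includes "primary language spoken at home, daycare attendance, and number of occupants in the home".

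**Models.** The primary LENA analysis is an ANCOVA with randomised group, age category and their interaction, "controlling for the baseline pre-measurement with a two-sided significance level of 0.05" (section 8a, Sample Size/Power Analysis, repeated in section 8d). The regression models linking reading environment and screen time to language scores name age and gender as covariates (section 8b). Section 8c states no stratification of the randomisation by home language.

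**The concern.** The rationale names bilingual children as the group whose scores could disturb the findings. The criterion excludes families who cannot manage the visit in English. These are different groups: a bilingual child usually has at least one caregiver who could pass the criterion. The factor that the protocol expects to matter therefore stays in the sample to some unknown degree.

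Two things are at stake. In the randomised comparison, a prognostic baseline factor left out of the model adds residual variance and leaves the estimate open to chance imbalance. If the arms then differ on home language, any adjustment would be chosen after the data are seen. In Hypothesis 2b, which relates ScreenQ to language scores, there is no randomisation to protect the comparison. Home language could confound it if it is also related to screen use.

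**Working it through.** **1. Criterion against rationale.** Take three homes:
- *No caregiver comfortable in English:* excluded.
- *Another language dominates, but the attending caregiver is comfortable and literate in English:* eligible.
- *Bilingual home, mainly English:* eligible.

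The rule removes the first kind of home, so it does reduce variation. It leaves the other two. That the survey still asks for primary home language is consistent with variation remaining.

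**2. The plan's own figure.** Inputs from section 8a: Cohen f = 0.30 (d = 2f = 0.6), two-sided alpha 0.05, power 80%, one baseline covariate. Noncentral F with 1 numerator df and noncentrality f²N gives N = 90 for one two-arm comparison (power 80.4%). Two age categories give 2 × 90 = 180, which matches. With 10% attrition, 180/0.90 = 200, which also matches. If 180 is instead read as serving one overall group effect, power is 97.9%. Home language enters neither calculation.

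**3. Assumptions.** The protocol gives neither the share p of children from homes with another language nor the difference b that remains after baseline adjustment. I take p = 0.20 to 0.50 and b = 0.3 to 0.5 residual SD.

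**4. Variance explained,** p(1 − p)b²:
- Low: 0.20 × 0.80 × 0.09 = 0.0144
- High: 0.50 × 0.50 × 0.25 = 0.0625

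**5. Equivalent gain in children,** 248/(1 − R²) − 248:
- Low: 248/0.9856 − 248 = 3.6
- High: 248/0.9375 − 248 = 16.5

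**6. Power with the term added, 90 children per age category.** From 80.4% to 80.9% (low) or 82.8% (high). The required number per category falls from 90 to 88 or 84.

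**7. Chance imbalance if the term is omitted.** The one-SD shift in the estimate is b × √(2p(1 − p)/n), with n per arm.

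| Basis | n per arm | Low | High |
|---|---|---|---|
| Whole trial | 124 | 0.3 × √(0.32/124) = 0.015 SD | 0.5 × √(0.50/124) = 0.032 SD |
| One age category | 62 | 0.3 × √(0.32/62) = 0.022 SD | 0.5 × √(0.50/62) = 0.045 SD |

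Against the design effect of 0.6 SD, the largest of these is 0.045/0.6 = 7.5%.

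**The case against.** **The rationale promises less than removal.** Section 15 speaks of minimising covariates, and excluding non-English-speaking families does that. Time, budget and the lack of a Spanish app are separate reasons. This stands: the exclusion is justified, and a reader who infers that the protocol claims to have eliminated home-language variation goes beyond its text. What remains is that the reason given concerns bilingual children, whom the criterion largely admits.

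**Covariates may be left to the SAP.** The SAP was not available, and the power paragraphs do not say that further covariates are barred. This has some force. But the protocol states its primary model twice and itself flags this factor as likely to matter. A later SAP term would also leave the rationale uncorrected.

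**Imbalance would be seen.** Section 8b plans group-wise comparisons that cover demographics. They would show an imbalance, but no adjustment is promised.

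**The item is a partial proxy.** A bilingual child in a mainly English home would be coded English. This stands and limits what the added term can achieve.

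**Stronger readings that the protocol does not support.** A reader might infer that the treatment comparison is biased. It is not in expectation, because home language precedes randomisation. A reader might infer that the study is underpowered as a result, but 180 reproduces without reference to home language. A reader might also argue that LENA at about 6 months adjusts poorly for home language. That is plausible, but no figure in the protocol bears on it, and section 8c describes the instrument as validated for infants and toddlers.

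**Conclusion.** The point holds, at low severity. The criterion limits the language in which the study is administered. It narrows home-language variation without removing it, and the variable collected on that variation is assigned to no stated model.

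For the primary comparison the cost is a little lost precision and some exposure to chance imbalance. On the assumed ranges these amount to about 1.4-6.3% of residual variance (about 4-17 of 248 children), and a one-SD shift of about 0.015-0.032 SD overall or 0.022-0.045 SD within one age category. All of this depends on p and b, which the protocol does not supply. Because the survey item captures bilingual exposure only partly, the real gain could be lower. For Hypothesis 2b the issue is possible confounding, whose size cannot be estimated from the document.

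**What to change.** 1. Prespecify primary home language (English versus other) as a covariate in the primary LENA ANCOVA, in sections 8a and 8d.
2. Add the same term to the ScreenQ-language regression for Hypothesis 2b in section 8b, alongside age and gender.
3. Reword section 15 to say that the criterion limits the language of administration and only reduces variation in home language.
4. State that the item is a partial proxy for bilingual exposure, so some of the effect will stay unadjusted.

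The cost is one term in each of two models and a few sentences. No new data are needed, and neither the sample size nor eligibility changes.
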